3.3 Study Design

The AF-FLOW Registry is a prospective, multi-center global post-market registry that will obtain clinical data in order to characterize the performance of the Ablamap Software for its intended use in a real-world setting. Specifically, we will evaluate the ability of the Ablamap Software to identify AF sources and guide ablation therapy in patients with atrial fibrillation. This registry will enroll up to 100 subjects. Subjects that present with atrial fibrillation and meet inclusion/exclusion criteria will be eligible for enrollment.

3.4 Enrollment/Screen Failures

A subject is considered enrolled after signing the informed consent. All enrolled subjects will then proceed to complete the screening and baseline tests.

3.5 Subject Follow-up

All subjects will be followed per protocol in relation to the date of the index ablation procedure. Follow up will be required at 12 months (± 45 days) post index ablation procedure. If a subject presents at any time during the 12-month follow-up period with recurrence of AF, the subject will be eligible for an EGF-guided ablation procedure. The follow-up schedule will remain the same and will not be reset if the patient requires a recurrence procedure.

Note: If any recurrences occur between any study procedures, cardioversion is allowed as often as needed. The number of cardioversions for each subject will be counted and reported.

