3.2 Study Endpoints

- Primary Efficacy Endpoint: Acute procedure success defined as the ability to successfully ablate AF sources identified by the Ablamap Software.
- Secondary Efficacy Endpoint: Freedom from documented episodes of AF recurrence following the blanking period (90 days post ablation) through 12 months.

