3.6 Statistical Analysis

The primary efficacy endpoint of this registry is the successful elimination of significant sources of excitation. Target parameter is the activity of the leading source. According to the retrospective data analyzed previously, the critical threshold for significance of a source is an activity of 26%.

Significance of the leading source will be tested in each patient at multiple times, in every procedure performed, in both atria, before and after PVI or PV touch-up and before and after ablation. The effect of targeted ablation will be statistically analyzed by determining the rate of reduction of leading source activity below threshold upon ablation. If an ablation is not successfully reducing the activity or if the location of the leading source changes upon ablation, ablation will be repeated.

The secondary endpoint of the study is freedom from documented episodes of AF recurrence following the blanking period (90 days post ablation) through 12 months.

We will analyze the level of significance of this difference based on the patients with sources above threshold that were successfully ablated and remained AF free versus those patients where no sources or sources below threshold were seen but were not ablated.

Descriptive summary statistics for continuous variables will include the number of subjects, mean, standard deviation or standard error, median, minimum, and maximum. Nominal categorical variables will be summarized using counts and percentages. Ordinal variables may be analyzed as if they were continuously scaled. Subject disposition, the number and percentage of subjects who complete and discontinue as well as reasons for early discontinuation will be presented. Demographic and baseline characteristics will be summarized descriptively.

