5.3 Pre-Procedure Requirements

Subjects should stop all AADs 48 hours prior to the procedure and be appropriately anticoagulated.

Regular amiodarone use should be discontinued at least 1 month prior to the index ablation procedure and not restarted after the ablation procedure.

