5.6 Blanking Period

The blanking period is the 90-day period following the index ablation procedure. During the blanking period, repeat ablation should not be performed; however, cardioversion may be done at the discretion of the investigator. **If the subject has a recurrence of AF during the blanking period and is placed on AADs, they should be discontinued from the AADs 90 days post ablation.**

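### Section 3.5 offers repeat EGF-guided ablation without the 90-day limit of 5.6, and the 12-month AF-freedom rate does not separate subjects who stay on an antiarrhythmic drug after day 90

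*Combined protocol and SAP*

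**What the plan says.** **Repeat ablation.** Section 3.5 (Subject Follow-up) says: "If a subject presents at any time during the 12-month follow-up period with recurrence of AF, the subject will be eligible for an EGF-guided ablation". It sets no earliest day and does not refer to 5.6. It adds: "The follow-up schedule will remain the same and will not be reset if the patient requires a recurrence procedure". Section 5.6 (Blanking Period) says: "The blanking period is the 90-day period following the index ablation procedure", and "During the blanking period, repeat ablation should not be performed"; cardioversion is allowed in that window. Section 3.6 also foresees more than one procedure per subject: "Significance of the leading source will be tested in each patient at multiple times, in every procedure performed".

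**Antiarrhythmic drugs.** Section 5.3 asks for all AADs to be stopped 48 hours before the procedure. On amiodarone it says: "Regular amiodarone use should be discontinued at least 1 month prior to the index ablation procedure and not restarted after the ablation procedure". Section 5.6 asks that AADs given for a recurrence in blanking be stopped 90 days after ablation.

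**Endpoint.** Section 3.2 defines the secondary efficacy endpoint as "Freedom from documented episodes of AF recurrence following the blanking period (90 days post ablation) through 12 months". The Protocol Summary and 3.6 define it in the same terms. None of the three mentions repeat ablation or AAD use.

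**The concern.** There are two separate issues.

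The first is an instruction that reads differently in two places. A site working from 3.5 alone could re-ablate a subject on day 60 and believe this was permitted. If that subject then has no documented AF after day 90, the endpoint records a success, although the index procedure was followed by an early recurrence and a second procedure.

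The second does not depend on anyone departing from the protocol. The AAD instructions in 5.3 and 5.6 show that the plan wants the outcome observed off drug, at least in part. The endpoint does not carry that intention through, and the instructions leave a group uncovered.

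This is the registry's only long-term outcome. A reader of the 12-month rate will want to know how much of it was reached with drug support, and the planned tables will not show that.

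**Working it through.** The plan gives no figure to reproduce: it has no expected rate of repeat ablation or AAD use, and no sample-size calculation. The check is a comparison of sections, followed by one line of arithmetic.

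**Step 1. Repeat ablation, by timing**

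| Situation | Instruction | Score under 3.2 |
|---|---|---|
| Lesions repeated within the index procedure | Required by 3.6: "If an ablation is not successfully reducing the activity or if the location of the leading source changes upon ablation, ablation will be repeated" | Not a separate procedure; not at issue |
| Separate procedure for AF before day 90, no AF documented later | Eligible under 3.5; advised against by 5.6 | Success |
| Separate procedure after day 90 for documented AF | Eligible under 3.5; outside the 5.6 window | Already a failure; not at issue |

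In the second row the clock is settled. Blanking is tied to the index procedure and the follow-up schedule is not reset, so the subject is not blanked again.

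**Step 2. AAD use after day 90, by route**

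| Route | Instruction | Score if no AF is documented after day 90 |
|---|---|---|
| Amiodarone restarted | Advised against by 5.3 | Success |
| AAD given for a recurrence in blanking, continued past day 90 | Advised against by 5.6 | Success |
| Another AAD resumed with no recurrence in blanking, continued past day 90 | None | Success |
| AAD started after day 90 for documented AF | None needed | Does not arise: already a failure |

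The third row is the gap in the instructions. Stopping all AADs 48 hours beforehand does not forbid resuming one afterwards. The first two rows are departures from conduct advice, and the endpoint does not register them either.

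**Step 3. Can the data show it?** Section 5.2 collects AAD history at baseline. Section 5.8 schedules medication assessment at baseline, index procedure, discharge and 12 months. Section 5.7.1 records AAD changes at 12 months. There is no scheduled visit near day 90, so use after that day must be reconstructed from start and stop dates. The case report forms are not in the documents, so whether they hold those dates has to be checked.

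**Step 4. Size.** Let N be the number of evaluable subjects and k the number who are AF-free after day 90 and belong to an affected row. Counting them as failures instead of successes changes the rate by

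100 × k / N percentage points.

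With N = 100, the planned maximum, this is k points. An affected subject with documented AF after day 90 contributes nothing, so the effect is at most 1 point per affected subject. If k were 5 (assumed), the change would be 100 × 5 / 100 = 5 points. The documents give no basis for any value of k.

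For scale, assume 60 of 100 subjects are AF-free, which is the upper end of the persistent-AF range in the Introduction. The 95% Wilson interval is 50.2% to 69.1%. Reclassifying two subjects gives 58 of 100, with interval 48.2% to 67.2%.

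**The case against.** The strongest reply is that nothing here is undefined. Section 3.5 says who is eligible and 5.6 says when, so a subject presenting on day 40 can be eligible then and treated after day 90. The endpoint also classifies everyone: documented AF after day 90 is a failure and its absence is a success. Counting AF-free subjects regardless of other treatment is a legitimate choice for a real-world registry. The protocol promises neither single-procedure nor off-drug freedom, it includes redo subjects, and the Introduction quotes persistent-AF results irrespective of added AADs.

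Most of this stands. A reader might infer that 3.5 and 5.6 flatly contradict each other; they can be reconciled, and what is missing is the limit or cross-reference in 3.5. A reader might infer that the endpoint lacks a rule for these subjects; it gives a definite answer, but one that pools them with subjects who are AF-free off drug after one procedure.

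A reader might also conclude that any repeat ablation should count as failure in the endpoint itself. That would replace the endpoint: it would fail subjects with no documented AF in the window and would catch ablation for other arrhythmias.

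Two things survive. The wording of 3.5 can still lead a site to re-ablate early, because 5.6 is only advisory. And the plan's AAD instructions have an aim that no planned analysis checks.

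**Conclusion.** The point holds as a minor, cheap improvement. Section 3.5 should carry the 90-day limit, and the 12-month rate needs a companion that separates drug-supported freedom from the rest.

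The effect is at most 1 point per affected subject with 100 evaluable subjects, and the number affected cannot be derived from the documents. If 5.6 is followed, the repeat-ablation part is probably small. The AAD part is unknown. The 1-point figure assumes that all 100 subjects are enrolled and evaluable; with fewer it becomes 100/N.

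The documents do not support a charge that the sponsor misstates the result, since no off-drug or single-procedure claim is made. Nor do they support a direction of bias in the 3.6 comparison of subjects with successfully ablated sources against those without sources above threshold: nothing indicates how AAD use or early re-ablation would divide between those groups.

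**What to change.** 1. In 3.5, allow a repeat EGF-guided ablation procedure only after the 90-day blanking period, and cite 5.6.
2. In 3.6, keep the overall AF-freedom rate as defined. Add a supporting rate in which use of a class I or III AAD after day 90 counts as failure, based on the medication data already collected. Check that the medication form captures AAD start and stop dates.
3. List any subject re-ablated for AF within blanking as a protocol deviation, and show the rate with those subjects counted as failures as a sensitivity analysis only. The endpoint is not redefined, and lesions repeated within the index procedure are not counted.

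The cost is one clause in 3.5, a short addition to 3.6, one extra table and a check of the forms. No new visit or test is needed, and protocol deviations are already in the 5.8 schedule. The downside is that the supporting rate may be slightly lower than the headline rate.

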3.6 Statistical Analysis

The primary efficacy endpoint of this registry is the successful elimination of significant sources of excitation. Target parameter is the activity of the leading source. According to the retrospective data analyzed previously, the critical threshold for significance of a source is an activity of 26%.

Significance of the leading source will be tested in each patient at multiple times, in every procedure performed, in both atria, before and after PVI or PV touch-up and before and after ablation. The effect of targeted ablation will be statistically analyzed by determining the rate of reduction of leading source activity below threshold upon ablation. If an ablation is not successfully reducing the activity or if the location of the leading source changes upon ablation, ablation will be repeated.

The secondary endpoint of the study is freedom from documented episodes of AF recurrence following the blanking period (90 days post ablation) through 12 months.

We will analyze the level of significance of this difference based on the patients with sources above threshold that were successfully ablated and remained AF free versus those patients where no sources or sources below threshold were seen but were not ablated.

Descriptive summary statistics for continuous variables will include the number of subjects, mean, standard deviation or standard error, median, minimum, and maximum. Nominal categorical variables will be summarized using counts and percentages. Ordinal variables may be analyzed as if they were continuously scaled. Subject disposition, the number and percentage of subjects who complete and discontinue as well as reasons for early discontinuation will be presented. Demographic and baseline characteristics will be summarized descriptively.

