Electrographic Flow (EGF) Mapping (Ablamap® Software, Ablacon, Wheat Ridge, CO) is an innovative technique to create full temporospatial visualizations of organized cardiac action potential flow within the chaotic conduction of AF that can discriminate between active sources of excitation and passive rotations, which do not generate action potentials; and can estimate the average activity of such a source during a time interval such as one minute.¹¹ It has been shown that only those sources that are generating excitation and that are active more than a quarter of the time are significant predictors for AF recurrence after PVI.¹² Using a 64-electrode basket mapping catheter, the software collects unipolar intracardiac EGMS. These EGMS are then processed using a proprietary algorithm employing Green's energy-optimizing formula to create a smooth landscape of voltage potentials for each sample point in time. An optical flow mapping algorithm is then applied to assemble these snapshots into a continuous recording of the excitation waves' behavior and propagation over time. The software also displays the dominant patterns of the excitation wave propagation recordings as vector flow maps, whose consistency over time can be measured and statistically analyzed (Figure 1):

Figure 1: Methodology of EGF Mapping

Ablacon has recently completed enrollment in the first randomized, controlled, clinical study to evaluate the Ablamap Software (FLOW-AF Study, NCT: NCT04473963). A total of 85 subjects were enrolled across four European centers. All subjects are being followed through twelve months, and the results will be available in late 2022.

The goal of this registry is to continue to evaluate the Electrographic Flow mapping software for identifying AF sources in patients to optimize ablation success in a real-world setting.

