2.2 Justification of Trial Design

The AF-FLOW Registry is a global post-market registry being conducted to collect clinical data to further characterize the performance of the Ablamap Software for its intended use. We also intend to continue to clinically validate the ability of the Ablamap Software to identify AF sources and guide ablation therapy in patients with atrial fibrillation.

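### Section 3.6 pools unablated no-source and sub-threshold subjects at a retrospective 26% cut and plans no analysis of recurrence by activity level

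*Combined protocol and SAP*

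**What the plan says.** - **The cut.** Section 3.6, citing earlier retrospective data: "the critical threshold for significance of a source is an activity of 26" percent. The protocol gives no derivation, confidence interval or sensitivity analysis for it.
- **Primary analysis.** Section 3.6 assesses targeted ablation by "determining the rate of reduction of leading source activity below threshold upon ablation".
- **Secondary comparison.** Section 3.6 sets "the patients with sources above threshold that were successfully ablated and remained AF free" against "those patients where no sources or sources below threshold were seen but were not ablated". Section 5.5 starts every procedure with a PVI, or a check of an earlier one, so I read not ablated as not ablated beyond PVI.
- **Rationale.** Section 1 says that only sources that generate excitation and are "active more than a quarter of the time are significant predictors for AF recurrence after PVI".
- **Aim.** Section 2.2 says the registry will "continue to clinically validate the ability of the Ablamap Software to identify AF sources".
- **Measurement.** Section 2.1 defines activity as a percentage of time. Section 3.6 has the leading source assessed several times per patient, in both atria, before and after ablation.
- **Procedure.** Section 5.5 sends above-threshold sources to ablation and repeats mapping until none is left above threshold. It lets investigators ablate no-source or sub-threshold subjects by their usual practice.

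**The concern.** The claim in section 1 has two sides: sources above roughly a quarter of the time matter, and weaker ones do not. Because section 5.5 directs above-threshold sources to ablation, what the registry can observe untreated is mostly activity below the cut. It can therefore speak mainly to the second side.

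Section 3.6 gives that question no output. Subjects with an untreated source just under 26% share a comparator with subjects who have no source, and activity is otherwise used only as above or below the cut. If weaker sources do carry risk, the pooled AF-free rate would be a blend whose value depends on the mix of the two types. At stake is the interpretation of the comparator and of the cut that also defines acute success.

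**Working it through.** The plan states no power, alpha, effect size or group sizes, and the data behind the 26% cut are not included, so there is no figure to reproduce. What follows is illustration on assumed inputs.

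**Inputs**
- No-source AF freedom at 12 months: 81.6%. Section 1 gives this figure for paroxysmal AF after PVI; using it for no-source subjects is an assumption.
- Sub-threshold AF freedom: 51% or 60%. Section 1 gives this range for persistent AF; using it here is likewise an assumption.
- Share w of sub-threshold subjects in the pooled group: 25%, 50% or 75% (assumed).
- Stratum size: 20 each (assumed; section 3.3 gives only a ceiling of 100 subjects overall).

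**Step 1: what pooling shows.** Pooled rate = (1 − w) × p_none + w × p_sub.

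| w | p_sub = 51% | p_sub = 60% |
|---|---|---|
| 25% | 0.75 × 81.6 + 0.25 × 51 = 74.0% | 76.2% |
| 50% | 66.3% | 70.8% |
| 75% | 58.7% | 65.4% |

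The underlying gap is 81.6 − 51 = 30.6 points, or 81.6 − 60 = 21.6 points. Neither appears in any planned output, and the plan does not commit to reporting w.

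**Step 2: what separate reporting could show.**
- Half-width of the 95% CI for one stratum: 1.96 × √(0.51 × 0.49 / 20) = 0.219, about ±22 points.
- Half-width for the difference between strata: 1.96 × √(0.816 × 0.184 / 20 + 0.51 × 0.49 / 20) = 0.277. The 30.6-point gap would be known to about ±28 points.
- Fisher exact power at 20 versus 20, two-sided 5%: 44% for 81.6% against 51%, and 23% for 81.6% against 60%.
- Subjects needed per stratum for 80% power (normal approximation, no continuity correction): 37 and 69.

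Separate strata would make a gap visible but would not test it reliably.

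**Step 3: does a continuous model remain usable with an ablation term?** Simulated registries of 100 were used, all inputs assumed: 20 subjects with no source; 20 unablated with activity 8% to 26%; 60 ablated with residual activity 0% to 26%; AF freedom falling in a straight line from 75% at zero activity to 45% at 26%. The logistic slope on final activity was significant in about 51% of registries with an ablation term and 52% without it, with false positives near 5% when there was no relationship. With a shallower fall, to 60% at 26% activity, the slope without the term was significant in about 19%. The term costs almost nothing, but power is modest at best. A straight-line relationship was built in, which favours this model.

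**The case against.** The best counter-argument is one of scope. The stated objective is to assess identification of sources and guidance of ablation, not to re-derive a threshold that section 5.5 treats as pre-specified. Nothing is lost either: activity is recorded in each patient, so the strata could be reported at any time. Both statements are true. But section 2.2 does claim continued validation, and strata chosen after the results are seen are weaker evidence than strata named beforehand.

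Several stronger readings are tempting, and the documents do not support them:
- **That both endpoints depend on the cut.** The primary analysis does. The secondary endpoint in section 3.2 is freedom from documented recurrence and contains no threshold; only its group comparison uses the cut.
- **That the comparator holds all the untreated sources.** Under section 5.5, mapping stops once nothing is above threshold, so ablated subjects may also keep untreated sub-threshold sources.
- **That ablated subjects would falsely match source-free ones.** As worded, the treated group is limited to subjects who stayed AF free, so its rate is 100% by construction. That is a separate and more serious flaw in the same sentence, and splitting the comparator does not cure it.
- **That 26% is wrong.** The retrospective data are not in the documents, so this cannot be judged.

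**Conclusion.** The point holds in limited form. Section 3.6 merges two groups that the threshold claim needs kept apart and plans no analysis of recurrence by activity, so its planned comparison is silent on whether untreated sources below 26% are associated with recurrence. On the assumed rates, a gap of 21.6 to 30.6 points would be hidden inside one pooled figure. The true gap, if any, and the true mix are unknown.

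This is a shortfall in planned analysis, not in data. The added results would be exploratory, because strata of about 20 are imprecise and investigators choose whom to ablate. They could inform the range below the cut. They could not by themselves validate 26%, since few sources above it should be left untreated.

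**What to change.** In section 3.6, report 12-month AF freedom with 95% CIs separately for:

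- (a) no source, not ablated beyond PVI;
- (b) sub-threshold source, not ablated beyond PVI;
- (c) no source or sub-threshold source, ablated at the investigator's discretion;
- (d) all above-threshold subjects who were ablated, whatever their later AF outcome.

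Add one pre-specified exploratory model of recurrence on leading-source activity from the final map of the index procedure, as a continuous variable with no source coded 0, and with a term for ablation beyond PVI. Report the slope with its 95% CI.

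The cost is a little more analysis work. No new patients, visits or measurements are needed, and no procedural rule changes. The report should state the imprecision and the confounding by non-randomised ablation. Restricting the treated group in the existing comparison to subjects who stayed AF free needs its own correction.

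### Section 3.6 does not say which procedure's maps feed the acute primary rate or assign the compared groups, although repeat procedures occur only after AF recurrence

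*Combined protocol and SAP*

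**What the plan says.** All references are to the combined protocol and SAP.

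- **Scope of the source assessment (3.6).** "Significance of the leading source will be tested in each patient at multiple times, in every procedure performed, in both atria". The next sentence says the effect of ablation will be analysed by "determining the rate of reduction of leading source activity below threshold upon ablation", the threshold being 26% activity. No unit (patient, procedure, atrium or source), denominator or restriction to the index procedure is given.
- **Route to a repeat procedure (3.5).** If a subject presents at any time in the 12 months "with recurrence of AF, the subject will be eligible for an EGF-guided ablation procedure". No other trigger is described. The clock is left alone: "The follow-up schedule will remain the same and will not be reset if the patient requires a recurrence procedure".
- **Groups compared (3.6).** One side is "patients with sources above threshold that were successfully ablated and remained AF free"; the other is introduced by "versus those patients where no sources or sources below threshold were seen but were not ablated". Neither definition names the procedure whose map or treatment decides membership.
- **Data collection (5.7 and 5.8).** The Schedule of Events lists procedural data and voltage maps under the index ablation procedure only. Recurrences go on an Unscheduled Visit CRF.

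**The concern.** A repeat EGF procedure is a consequence of the outcome that the secondary endpoint measures. If its maps count in the analysis, events after the index procedure help to decide which procedures enter the primary rate and who stays in a comparison group.

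For the primary endpoint, the rate would no longer describe the index procedure. It would be a blend weighted towards patients who did badly, each contributing at least twice. For the secondary comparison, subjects could leave the comparator because they recurred, while those who stayed AF-free could not leave by that route. The comparator would then look better than the subjects who entered it. Since the rule is not written down, the choice could also be made after the data are seen.

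**Working it through.** The plan gives no alpha, power or sample-size derivation (3.3 says only up to 100 subjects), so there is no figure of its own to reproduce. The check is a reading of the sections together, followed by two illustrations.

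**Step 1: do other sections fix the rule?** Section 5.6 counts blanking from the index ablation, and 3.5 does not reset follow-up. Both concern clocks, not group assignment or the acute denominator. Section 5.8 schedules procedural data at the index procedure only, which does not match the every-procedure scope in 3.6. The redo subjects in 5.5 had their PVI before enrolment, so their registry procedure is their index procedure and they are not an exception. The rule is therefore unstated.

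**Step 2: recurrence-selected procedures in the primary rate.**

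Inputs:
- N = 100, the upper limit in 3.3. For simplicity every index procedure is taken to contribute.
- Recurrence of 18.4%, 40% or 49%, the complements of the 81.6%, 60% and 51% quoted in section 1.
- Assumed: 25% to 75% of recurrers have a repeat; acute success is 90% at index and 50% to 70% at repeats.

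Formulas: repeats r = N × recurrence × repeat share; fraction of all procedures = r/(N + r); pooled rate = (N × p_index + r × p_repeat)/(N + r).

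- Low end: r = 100 × 0.184 × 0.25 = 4.6; fraction 4.6/104.6 = 4.4%; pooled (90 + 0.7 × 4.6)/104.6 = 89.1%.
- High end: r = 100 × 0.49 × 0.75 = 36.75; fraction 36.75/136.75 = 26.9%; pooled (90 + 0.5 × 36.75)/136.75 = 79.3%.

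A smaller example, also assumed throughout: 51/60 = 85% at index and 7/12 at repeats give 58/72 = 80.6%.

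**Step 3: comparator AF freedom.** Let the comparator have n subjects with true AF freedom f, and let a fraction q of its recurrers leave because a source is ablated at a repeat. The AF-free count n × f is unchanged and the denominator falls to n − q × n × (1 − f). The reported rate is f/(1 − q(1 − f)), which does not depend on n or on where the departing subjects are then placed.

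Worked case (assumed): n = 40 and f = 60%, so 24 are AF-free and 16 recur. Eight of the 16 have a repeat, and 5 of those have a source ablated. The rate moves from 24/40 = 60% to 24/35 = 68.6%.

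Over a wider assumed range:

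| True AF freedom | q = 25% | q = 50% |
|---|---|---|
| 51% | 58.1% | 67.5% |
| 60% | 66.7% | 75.0% |
| 81.6% | 85.5% | 89.9% |

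**Step 4: under an index-only rule.** No recurrence-selected procedure enters the primary rate and no subject leaves the comparator because of recurrence. The worked case stays at 24/40 = 60%.

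**The case against.** The strongest reply is that 3.6 says the leading source will be tested in every procedure. That describes measurement; it is not a pooling rule. The Schedule of Events and the Unscheduled Visit CRF also point towards an index-based analysis. This stands in part: the plan cannot be said to pool procedures expressly or to reassign groups from repeat maps. But nothing excludes either. The sentence on the rate follows directly from the every-procedure sentence, so including repeats is the natural reading.

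A second reply concerns the ablated group, and it stands in full. A reader might infer that a source-negative subject who recurs and is ablated at a repeat moves into that group, or that an index acute failure enters it after a successful repeat. Such a reader might then calculate a spurious difference. If the five subjects above joined an assumed source-positive group of 60, it would show 36/65 = 55.4%, or 41/65 = 63.1% if they were counted AF-free after the repeat. Against 68.6% these are differences of about −13 and −5.5 points. The documents do not support this. Group 1 consists of "patients with sources above threshold that were successfully ablated and remained AF free", and read literally the last condition keeps recurrers out. Those figures also ignore the requirement of successful ablation. Entry would need a recurrence inside blanking or an AF-free period restarted at the repeat. Section 5.6 starts blanking at the index ablation and 3.5 does not reset follow-up, which makes a restart unnatural. Section 3.5 allows a repeat at any time, whereas 5.6 says repeat ablation should not be done during blanking; these two passages must be reconciled.

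A third reply also stands: an index-only rule does not by itself rescue the comparison. A group defined by remaining AF-free is 100% AF-free whichever map assigns it.

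Finally, this is a post-market registry with no stated success criterion, and the size of any bias rests on assumptions. That limits the claim about size, but not the claim that the rule is missing.

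**Conclusion.** The concern holds as an unstated rule with two consequences on a natural reading. The acute primary rate can include repeat procedures from recurrence patients only, counting those patients more than once. The comparator can lose recurrers and only recurrers, which inflates its AF freedom.

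In the worked case the inflation is 8.6 points (60% to 68.6%). Over the range in the table it is about 4 to 16.5 points. For the primary rate, an assumed 90% becomes 79.3% to 89.1%, but only if repeats succeed less often than index procedures, which the documents do not say. Group sizes, repeat rates, repeat findings and acute success rates are all assumptions.

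The upward direction for the comparator rests on counting sources and ablations from any procedure. If the latest map alone decided membership, an ablated subject who recurred and had no source at the repeat could be placed in the comparator, and the bias would run the other way. No between-group bias of known size or sign can be claimed from the plan as written.

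**What to change.** In section 3.6:

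1. State that the acute primary endpoint is one result per subject, taken from the index procedure.
2. State that the compared groups are assigned only from the index-procedure maps and the treatment given at the index procedure.
3. Remove the AF-free condition from the ablated group's definition, so that AF freedom is the outcome compared between groups. Without this step, items 1 and 2 do not give a fair comparison.
4. Report source findings and acute results at repeat procedures in a separate descriptive table that sets source status at index against status at repeat.

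Align the Schedule of Events with this, so that it shows where repeat-procedure data are recorded if the table is to be produced.

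The cost is about a paragraph of wording, with no change to patient care and no data beyond what 3.6 already foresees. The one real loss is that repeat-procedure results no longer contribute to the primary rate.
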